 - Oxygen saturation (# of episodes of oxygen desaturation below 90% per hour).
 - *Respiratory Distress Index* - The sum of the following parameters calculated per hour of wakefulness: 1) number of breath-holding episodes, 2) number of episodes of hyperventilation [1 and 2 are as defined in inclusion criteria; each would have to be ≥ 10 seconds in duration], and 3) number of drops in oxygen values to $< 90\%$.
- **Rett Syndrome Clinical Severity Scale (RCSS):** frequency and manageability of seizures, respiratory irregularities, scoliosis, ability to walk (gait apraxia), hand use, speech and sleep; yielding total and feature-specific scores.
- Efficacy in patients with a sarizotan plasma concentration of >400 ng/mL on Day 15.

Pharmacokinetics – Secondary Objective

Blood samples for measurement of plasma levels of sarizotan and its major metabolites and determination of PK parameters will be collected just prior to the first dose of Dose Level 1 (blank sample) and at approximately 1 and 4 hr post-dose (± 15 min) on Day 1. On Day 15, a blood sample will be taken prior to dosing on Day 15 (trough level for Dose Level 4) and at 1 and 4 hr post-dose (Dose Level 4).

Details of the population PK analysis and determination of dose-proportionality for sarizotan will be provided in a separate document.

Safety Monitoring Board

Safety data from all patients will be examined periodically by an Independent Safety Monitoring Board (ISMB). The ISMB may request modifications to the study design or request that the study be terminated, should any significant safety concerns become evident.

Statistical Methods:

Sample Size:

A minimum of 129 patients with RTT will be included in this study, with approximately equal numbers of patients randomly assigned to each of the three treatment groups:

- low dose sarizotan [sarizotan 2 mg *bid* (age 4 to <13 years; or age \geq 13 years, weight <25 kg) or 5 mg *bid* (age \geq 13 years, weight \geq 25 kg)],
- high dose sarizotan [sarizotan 5 mg *bid* (age 4 to <13 years; or age \geq 13 years, weight <25 kg), or 10 mg *bid* (age \geq 13 years, weight \geq 25 kg)],
- or placebo *bid*.

The sample size estimate was based on the following assumptions:

- 3 treatment groups (2 active + placebo)
- Primary endpoint: Percent reduction in the number of apnea episodes (\geq 10 sec each) per hour
- H_0 : Percent reduction in apnea episodes in placebo and active groups is the same
- H_A : There is a difference in the % reduction in apnea episodes between high dose sarizotan and placebo.

The assumptions for the estimated standard deviation (SD) are based on limited data from a study by [Khawaja et al. \(2014\)](#), in RTT patients. There were only 5 patients with data reported for apnea index (for apnea episodes \geq 10 seconds). Pilot observational data collected using the BioRadio device in 26 patients with RTT indicated that the number of episodes of apnea may approach 60 per hour. Based on the range of 10-60 episodes per hour, ranges of 10-30, 10-45 and 10-60 apnea episodes per hour indicate SDs of 5.0, 8.75 and 12.5, respectively.

Sample sizes were computed to determine the number of patients required to detect a minimum difference in mean percent reduction of 20% (high dose sarizotan 30%, placebo 10%) and 10% (high dose sarizotan 20%, placebo 10%), based on differences between high dose sarizotan and placebo.

Sample sizes of 23 or 34 in each treatment group will have 90% power to detect a difference in mean percent reduction of -20% or -10%, respectively, assuming a common SD of 20 (for the 20% reduction) and 12.5 (for the 10% reduction), using a two-group t-test with a 0.050 two-sided significance level. Assuming an attrition rate of 25% (7 or 9 patients) per group, a total of 30 or 43 patients would need to be enrolled in each group to get 23 or 34 patients completing the study. As this is the first large-scale study evaluating the effect of sarizotan on respiratory symptoms in patients with RTT, a conservative estimate of 10% reduction in apnea episodes was used to estimate the sample size required, i.e. approximately 43 patients per group.

The sample size may be revised based on a prospective assessment of variability in the frequency of apnea episodes, of 10 seconds or greater duration, from data collected from the first 20 patients who complete screening.

Subject Characteristics:

The background and demographic characteristics (age, race, ethnicity, weight, height, education, past and current medical conditions, etc.), disease characteristics, and prior/concomitant medication use for randomized patients will be summarized by treatment group. Continuous variables will be summarized by minimum, maximum, mean, median, and standard deviation, and discrete variables will be summarized using frequencies and percentages.

Safety Analysis:

The safety population will consist of all subjects who took at least one dose of study medication. All AEs will be summarized by body system and preferred term. The incidence (%) of SAEs, AEs that are newly occurring or worsened after administration of study medication (i.e. treatment-emergent AEs [TEAEs]), and AEs leading to discontinuation (ADOs) will also be summarized; severity of each AE and relatedness to study medication will be

assessed and presented. Changes from baseline in vital signs, ECG and laboratory values, and findings on physical, neurological and routine ophthalmology examinations will be summarized, with abnormal and clinically notable values/findings being identified. In the initial 24-week, double-blind, placebo-controlled period, a comparison will be made between the sarizotan and placebo groups in the proportion of patients experiencing SAEs, ADOs, TEAEs and any clinically significant abnormalities in other safety parameters. Where feasible, mean changes from baseline will be examined using a paired t-test. Safety data for the open-label extension period will be analyzed separately and will use the Week 24 evaluations from the double-blind period as the baseline assessments.

Efficacy Analysis:

Primary Efficacy Outcome. The primary efficacy analysis for the initial, 24-week, double-blind, treatment period will be performed on the Intent-to-Treat (ITT) population, consisting of all patients who were randomized to treatment. The percent reduction (change) from baseline in the number of apnea episodes (each ≥ 10 seconds in duration) per hour, during awake time, will be compared between treatment groups using a Mixed Model Repeated Measures (MMRM) analysis. The MMRM model will include percent change from baseline as response, the fixed, categorical effects of treatment group, visit, treatment group-by-visit interaction, and the continuous terms age and baseline value as covariate. A statistically significant difference between high dose sarizotan (5 or 10 mg *bid*) and placebo will be considered evidence of efficacy in reducing apnea.

Key Secondary Efficacy Outcome. The mean rating of the caregiver-rated CIC at Week 24/endpoint will be compared between treatment groups using the Van Elteren test (a stratified Cochran Mantel Haenszel test with modified ridit scores). The following age strata will be considered in the analysis: < 13 years and ≥ 13 years. In addition to the above analysis, comparisons between treatments for the proportion of patients rated improved at Week 24 will be done using logistic regression.

Other Secondary Efficacy Outcomes.

The analysis of the Caregiver Top 3 Concerns will be performed first, comparing the change from baseline in the total score on the VAS for each of the 3 symptoms identified as most concerning at baseline using an ANCOVA-LOCF analysis. The model will include treatment group and the baseline value along with age as covariates. Change will be estimated using the least-squares mean derived from the ANCOVA. Comparisons between treatment groups at Week 24 will be made using the difference in least-squares mean, 95% confidence interval (CI) and p-values from the ANCOVA model.

Descriptive statistics will be presented for the other secondary efficacy outcomes. The proportion of patients rated improved, as well as the mean score, on the Investigator-rated CGI-C at each of the scheduled visits will be presented. Actual values and the change from baseline in other secondary efficacy variables (Motor Behavioral Assessment Scale and subscales, other respiratory parameters, and RCSS) at all scheduled visits will be presented. An additional analysis of efficacy will be performed for patients with a sarizotan plasma concentration of > 400 ng/mL.

Multiple comparisons/ multiplicity.

The study level error rate will be controlled by following a sequential multiple testing procedure, where testing will begin with the primary efficacy endpoint. The effects of the high dose sarizotan versus placebo will be analyzed first for all parameters in a pre-specified sequence.

The sequence of testing will be as presented below:

- Percentage change from baseline in the number of apnea episodes,
- Mean rating of CIC,
- Mean change from baseline in the Top Three Concerns Total Score.

Initial 24-week Double-Blind Treatment Period. The primary efficacy assessment for the study will be performed using data from the initial 24-week double-blind, placebo-controlled treatment period. A statistical “Win” will be claimed if the following results are obtained in the primary and key secondary efficacy analyses:

- Statistically significant difference between high dose sarizotan (5 or 10 mg *bid*) and placebo in the percent reduction (change) from baseline in the number of apnea episodes (each ≥ 10 seconds in duration) per hour, during awake time;
- Directional change on the CIC in favor of high dose sarizotan (5 or 10 mg *bid*) compared to placebo.

168-week Open-label Extension. Efficacy data from the extension period obtained from patients randomized to sarizotan at Baseline will be analyzed to determine if there is any attenuation of the benefit noted during the first six months. The response in placebo patients switched to sarizotan in the extension period will be compared with that in patients who were treated with sarizotan throughout the study.

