1 SYNOPSIS

Title of Study: A Randomized, Double-Blind, Placebo-Controlled, Six-Month Study to Evaluate the Efficacy, Safety and Tolerability of Sarizotan in Patients with Rett Syndrome with Respiratory Symptoms

Protocol No.: Sarizotan/001/II/2015

Phase of Development: II/III

Objectives:

The objectives of the study are as follows:

Primary Efficacy Objective:

- To evaluate the effect of sarizotan (high dose), compared to placebo, on reducing the number of apnea episodes, during awake time, in patients with RTT with respiratory abnormalities.

Key Secondary Efficacy Objective:

- To evaluate the effect of sarizotan (high dose), compared to placebo, on the Caregiver-rated Impression of Change (CIC) from baseline;

Secondary Objectives:

- **Safety:** To evaluate the safety and tolerability of sarizotan in patients with Rett syndrome (RTT) with respiratory abnormalities.
- **Efficacy:** To evaluate the efficacy of sarizotan, compared to placebo, on the following:
 - Severity of patient symptoms, based on evaluation of Caregiver Top 3 Concerns (Visual Analogue Scale [VAS]);
 - Global change from baseline, assessed by the Clinical Global Impression of Change (CGI-C);
 - Motor behavior, assessed by the Motor-Behavioral Assessment Scale;
 - Other respiratory symptoms of Rett syndrome, assessed during awake time, including:
 - Percent time spent with breathing dysrhythmia (% time apnea + % time hyperventilation) per hour;
 - Number of hyperventilation episodes (≥ 10 seconds each) per hour;
 - Oxygen saturation (number of episodes of oxygen desaturation below 90% per hour).
 - *Respiratory Distress Index* - The sum of the following parameters calculated per hour of wakefulness: 1) number of breath-holding episodes, 2) number of episodes of hyperventilation [1 and 2 are as defined in inclusion criteria; each would have to be ≥ 10 seconds in duration], and 3) number of drops in oxygen values to $< 90\%$.
 - Overall assessment of symptoms of RTT using the Rett syndrome Clinical Severity Scale (RCSS).
 - To determine the efficacy of sarizotan in patients who attain a minimum plasma exposure of 400 ng/ml on Day 15 (expected efficacious concentration based on the knockout mouse model);
- To determine the pharmacokinetic (PK) profile of sarizotan at the doses tested and compare with the PK profile in adults.

Study Design and Methods:

Initial 24-Week Double-blind Treatment Period

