8 STUDY OBJECTIVES

The objectives of the study are as follows:

Primary Efficacy Objective:

- To evaluate the effect of sarizotan (high dose), compared to placebo, on reducing the number of apnea episodes, during awake time, in patients with RTT with respiratory abnormalities.

Key Secondary Efficacy Objective:

- To evaluate the effect of sarizotan (high dose), compared to placebo, on the Caregiver-rated Impression of Change (CIC) from baseline;

Secondary Objectives:

[figure not shown]
- Safety: To evaluate the safety and tolerability of sarizotan in patients with Rett syndrome (RTT) with respiratory abnormalities.
- Efficacy: To evaluate the efficacy of the dose range of sarizotan, compared to placebo, on the following:
 - Severity of patient symptoms, based on evaluation of Caregiver Top 3 Concerns (Visual Analogue Scale [VAS]);
 - Global change from baseline, assessed by the Clinical Global Impression of Change (CGI-C);
 - Motor behavior, assessed by the Motor-Behavioral Assessment Scale;
 - Other respiratory symptoms of Rett syndrome, assessed during awake time, including:
 - Percent time spent with breathing dysrhythmia (% time apnea + % time hyperventilation) per hour;
 - Number of hyperventilation episodes (≥ 10 seconds each) per hour;
 - Oxygen saturation (number of episodes of oxygen desaturation below 90% per hour).
 - *Respiratory Distress Index* - The sum of the following parameters calculated per hour of wakefulness: 1) number of breath-holding episodes, 2) number of episodes of hyperventilation [1 and 2 are as defined in inclusion criteria; each would have to be ≥ 10 seconds in duration], and 3) number of drops in oxygen values to $< 90\%$.
 - Overall assessment of symptoms of RTT using the Rett syndrome Clinical Severity Scale (RCSS).
 - To determine the efficacy of sarizotan in patients who attain a minimum plasma exposure of 400 ng/ml on Day 15 (expected efficacious concentration based on the knockout mouse model);
- To determine the pharmacokinetic profile of sarizotan at the doses tested and compare with the pharmacokinetic profile in adults.

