2.2. SECONDARY OBJECTIVES

- Key Secondary efficacy: To evaluate the effect of sarizotan (high dose), compared to placebo, on the Caregiver-rated Impression of Change (CIC) from baseline.
- Safety: To evaluate the safety and tolerability of sarizotan in patients with Rett syndrome (RTT) with respiratory abnormalities.
- Efficacy: To evaluate the efficacy of sarizotan, compared to placebo, on the following:
 - Severity of patient symptoms based on evaluation of Caregiver Top 3 Concerns (Visual Analogue Scale [VAS]); Global change from baseline, assessed by the Clinical Global Impression of Change (CGI-C);
 - Motor behavior, assessed by the Motor-Behavioral Assessment Scale;

Document:	\\ieedc-vnasc01\BIOSdata\Newron\Sarizotan\PXA76395\Biostatistics\Documentation\SAP		
Author:	[name]	Version Number:	V2
		Version Date:	[30March2020]
Template No:	CS_TP_BS016 – Revision 4	Reference:	CS_WI_BS005
Effective Date:	01Apr2016		

- Other respiratory symptoms of Rett syndrome, assessed during awake time, including:
 - Percent time spent with breathing dysrhythmia (% time apnea + % time hyperventilation) per hour
 - Number of hyperventilation episodes (≥ 10 seconds each) per hour
 - Oxygen saturation (number of episodes of oxygen desaturation below 90% per hour).
 - *Respiratory Distress Index* - The sum of the following parameters calculated per hour of wakefulness: 1) number of breath-holding episodes, 2) number of episodes of hyperventilation [1 and 2 are as defined in inclusion criteria; each would have to be ≥ 10 seconds in duration], and 3) number of drops in oxygen values to $< 90\%$.
- Overall assessment of symptoms of RTT using the Rett syndrome Clinical Severity Scale (RCSS);
- To determine the efficacy of sarizotan in patients who attain a minimum plasma exposure of 400 ng/ml on Day 15 (expected efficacious concentration based on the knockout mouse model);
- To determine the PK profile of sarizotan at the doses tested and compare with the PK profile in adults.

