15.2.2 MISSING DATA METHODS FOR SECONDARY EFFICACY VARIABLES

Last observation carried forward (LOCF) method will be adopted as imputation in the presence of at least one post-baseline observation if data is collected at multiple visits post baseline and is missing. Missing items in, Top 3 concerns score at baseline will be imputed with the mean baseline value of that item of all patients in the analysis population. There will be no imputation for MBAS, RCSS and Other Respiratory symptoms of RTT since only descriptive summary is presented.

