15.2.3 ANALYSIS OF SECONDARY EFFICACY VARIABLES

15.2.3.1 Analysis of Caregiver Top 3 Concerns Total Score at Week 24

Descriptive statistics will be presented for actual value, change from baseline and percentage change from baseline in Top 3 Concerns total score by visit and treatment groups.

Document:	\\ieedc-vnasc01\BIOSdata\Newron\Sarizotan\PXA76395\Biostatistics\Documentation\SAP		
Author:	[name]	Version Number:	V2
		Version Date:	[30March2020]
Template No:	CS_TP_BS016 – Revision 4	Reference:	CS_WI_BS005
Effective Date:	01Apr2016		

Comparisons between treatments will be done using an ANCOVA model. The model will include treatment group and the baseline value along with age as covariates. Change will be estimated using the least-squares mean derived from the ANCOVA. Comparisons between treatment groups at Week 24 will be made using the difference in least-squares mean, 95% confidence interval (CI) and p-values from the ANCOVA model.

Additional summaries of the Top 3 Concerns will be presented as follows:

- i. Frequency and percentage of all Top 3 Concerns reported.
- ii. Mean change and percent change from baseline for each Top 3 Concern reported.
- iii. The number and percentage of patients with at least a 20% improvement in the Top 3 Concerns Total Score.

Additionally, graphical presentation will be provided.

15.2.3.2 Analysis of mean rating of Clinical Global Impression of Change (CGI-C) at Week 24

Summary statistics for the proportion of responders on the CGI - C (n, count, and percent) will be presented at all available scheduled visits for 24-week double-blind treatment period as per protocol.

Summary statistics will also be presented for the CGI-C mean change score and summarized by visit. Additionally, graphical presentation will be provided.

15.2.3.3 Analysis of change from baseline to Week 24 in Motor-Behavioral Assessment Scale (MBAS)

Descriptive statistics will be presented by treatment group for actual and change from baseline in Motor-Behavioral Assessment scale, both for subtotals and grand total at all available scheduled visits for the 24-week double-blind treatment period, as per protocol.

15.2.3.4 Analysis of change from baseline to Week 24 in other respiratory symptoms of RTT

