Descriptive statistics will be presented by treatment group for actual values and change (or percent change) from baseline in other respiratory symptoms of RTT for both BioRadio™ and SOMNOtouch (*Refer to Section 15.2.1.4 for list of other respiratory symptoms*) at all available scheduled visits for the 24-week double-blind treatment period, as per protocol. Data from the Bio-Radio and the SOMNOtouch will not be pooled and will be analyzed separately.

Document:	\\ieedc-vnasc01\BIOSdata\Newron\Sarizotan\PXA76395\Biostatistics\Documentation\SAP		
Author:	[name]	Version Number:	V2
		Version Date:	[30March2020]
Template No:	CS_TP_BS016 – Revision 4	Reference:	CS_WI_BS005
Effective Date:	01Apr2016		

15.2.3.5 Analysis of change from baseline to Week 24 in Rett syndrome Clinical Severity Scale (RCSS)

Descriptive statistics will be presented by treatment group for actual score and change from baseline in the Rett syndrome Clinical Severity Scale (RCSS) at Week 24 of the double-blind treatment period, as per protocol.

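### Four secondary outcome families have a placebo-comparison objective but get only by-arm descriptive summaries, with no pre-specified adjusted between-arm estimate or interval

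*Protocol*

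**What the plan says.** **Objective.** The Protocol Synopsis introduces the list of secondary efficacy outcomes with "To evaluate the efficacy of sarizotan, compared to placebo, on the following". Protocol section 8 has "To evaluate the efficacy of the dose range of sarizotan, compared to placebo, on the following", which brings in both doses. SAP section 2.2 repeats the comparison: "Efficacy: To evaluate the efficacy of sarizotan, compared to placebo, on the following". Each list contains Top 3 Concerns, CGI-C, motor behaviour, the other respiratory measures and the RCSS.

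**Analysis.** Apart from Top 3 Concerns, the Synopsis and Protocol section 15.2.6 say "Descriptive statistics will be presented for the other secondary efficacy outcomes". In the SAP:

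- CGI-C (15.2.3.2): "Summary statistics for the proportion of responders on the CGI - C (n, count, and percent) will be presented", plus mean scores by visit.
- MBAS (15.2.3.3): "Descriptive statistics will be presented by treatment group for actual and change from baseline in Motor-Behavioral Assessment scale".
- Other respiratory measures (15.2.3.4): "Descriptive statistics will be presented by treatment group for actual values and change (or percent change) from baseline in other respiratory symptoms of RTT", with BioRadio and SOMNOtouch kept apart.
- RCSS (15.2.3.5): the same kind of by-arm summary at Week 24.

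**Missing data.** SAP 15.2.2 states: "There will be no imputation for MBAS, RCSS and Other Respiratory symptoms of RTT since only descriptive summary is presented".

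**The concern.** The objective asks how sarizotan differs from placebo; the planned output describes each arm separately. For these outcomes no estimate of the difference is defined, so neither the adjustment, the handling of missing visits nor an interval is fixed in advance. Any contrast reported later would have its form chosen after the data are seen.

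Percent time in dysrhythmia, desaturation and the Respiratory Distress Index are what would show whether fewer apneas mean better breathing overall. The rationale in Protocol section 7.3 itself points to apneas accompanied by saturation below 90% as clinically meaningful. CGI-C, MBAS and RCSS carry the clinician's view of benefit. Readers will compare the arm columns whatever the plan calls them.

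**Working it through.** **1. Does any other clause supply the comparison?**

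| Clause | What it supplies for these outcomes |
|---|---|
| SAP 6.4 | Comparator, two-sidedness and alpha for tests; assigns no test or estimate to them |
| SAP 7.1 | Baseline and age adjustment where applicable; no model is specified here |
| SAP 7.4 | Sequence of apnea, CIC and Top 3 Concerns only |
| SAP 7.5 | Age subgroups, without inference |
| SAP 15.2.4 | Plasma-threshold analysis of the primary endpoint; further exposure-response work is unspecified |
| SAP 3.3 | No changes from the protocol |

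None fills the gap. By contrast, Top 3 Concerns, from the same objective list, gets an ANCOVA difference in LS means with 95% CI and p-value (SAP 15.2.3.1).

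**2. Which summaries are observed-case?** SAP 15.2.2 exempts MBAS, RCSS and the other respiratory measures from imputation. CGI-C is not named there, so the general LOCF rule in that section could apply. The opening of SAP 15.2 attaches LOCF to Top 3 Concerns and lists the CGI-C section without it. SAP 7.3 refers the reader to the endpoint's own section, which is silent. CGI-C is therefore unresolved.

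**3. Would an interval be useful at the planned size?** First the plan's own figure: a difference of 10, SD 12.5, two-sided 0.05 and 90% power (Protocol 15.2.8) give 34 per group by the two-sample t-test, with power 90.2%. This reproduces.

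For a continuous outcome, the 95% half-width in SD units is t × √(2/n), multiplied by √(1 − r²) if baseline, with correlation r to the outcome, is a covariate.

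| n per arm | Unadjusted | r = 0.3 | r = 0.5 | r = 0.7 |
|---|---|---|---|---|
| 34 | 0.48 | 0.46 | 0.42 | 0.35 |
| 43 | 0.43 | 0.41 | 0.37 | 0.31 |

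The values of r are assumptions. Taking 25% attrition from 43 leaves 43 × 0.75 ≈ 32 per arm, with an unadjusted half-width of 0.50 SD.

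For the CGI-C responder difference, 1.96 × √(2p(1 − p)/n) gives 22 to 24 percentage points at n = 34 and 19 to 21 at n = 43, for assumed rates p of 30% to 50%.

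**4. How far could a crude difference of observed-case means be off?** The simulation used 4000 trials per setting, no drug effect, 43 per arm, 25% dropout after Week 8 and standardised outcomes with equal correlation ρ between visits. Response-driven dropout has weight exp(1.5 × Week 8 change), so patients doing worse leave more often. Bias is given in SD units, negative favouring sarizotan.

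| Method and dropout pattern | ρ = 0.4 | ρ = 0.6 | ρ = 0.8 |
|---|---|---|---|
| Observed cases; response-driven on sarizotan, random on placebo | −0.18 | −0.13 | −0.07 |
| Observed cases; same response-driven pattern in both arms | about 0 | about 0 | about 0 |
| Completer ANCOVA on baseline; response-driven on sarizotan only | −0.07 | −0.08 | −0.06 |

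In the first pattern, a model using baseline and Week 8 had bias near zero. That follows by construction, because dropout depended only on an observed visit. Its standard error was smaller: 0.236 against 0.275, 0.202 against 0.222, and 0.150 against 0.160 SD, a gain of 6 to 14%.

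**5. Where can a model use earlier visits?** BioRadio measures are taken at Weeks 2, 8, 16 and 24, and MBAS at Weeks 8, 16 and 24, so it can. RCSS has one scheduled post-baseline rating, so it cannot. SOMNOtouch has Weeks 16 and 24 but no Week 8. CGI-C is itself a rating of change and has no baseline score.

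**The case against.** The strongest reply is that the choice is deliberate and consistent across both documents. Inference is confined to three ordered endpoints, the win rule rests on apnea and CIC, and no claim is attached to these outcomes. Descriptive reporting below a gatekept sequence is legitimate. That stands: this is not a type I error problem, and no p-values are called for. It does not answer the wording of the objective, which still asks for a comparison.

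Three stronger readings are tempting and are not supported:

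- *The trial could say nothing about the size or uncertainty of these effects.* The tables give n, mean and SD by arm, and counts for CGI-C responders, from which an unadjusted difference and interval can be computed. What is missing is a pre-specified, adjusted one.
- *All the listed outcomes are observed-case.* The SAP says so only for MBAS, RCSS and the other respiratory measures.
- *The tables will favour sarizotan.* The bias in the working needs dropout that depends on response differently by arm, and nothing in the documents predicts that. The 25% is a sizing assumption. Patients who stop early are also asked to complete the Week 24 assessments (Protocol 9.2.4), although SAP 8.2 assigns visits by study day, so an early stopper's ratings may fall in an earlier window.

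A further fair objection is that one Gaussian repeated-measures model for everything would be a poor prescription. It does not suit a 7-point rating, for which the plan's matching CIC scale uses a Van Elteren test and logistic regression, and it cannot repair dropout for RCSS. This is accepted and narrows the fix.

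**Conclusion.** The mismatch holds in both documents. Four outcome families have a comparative objective and no pre-specified between-arm estimate. The defect is one of estimation and clarity. It does not touch error control, the primary analysis or the win rule.

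The textual finding rests on no numerical assumption. The possible bias in a crude comparison does: about 0.07 to 0.18 SD under response-driven dropout on sarizotan only, and about zero under the null when dropout is the same in both arms. It should be read as a sensitivity range, not a forecast. The precision argument is firmer: at the planned size, unadjusted intervals of about ±0.43 to 0.48 SD could be reported, and narrower ones if baseline is correlated with outcome. The change is worth making, at moderate priority.

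**What to change.** Keep the descriptive tables. In SAP 15.2.3.2 to 15.2.3.5 and Protocol 15.2.6, add Week 24 differences from placebo for each dose group with 95% CIs, without p-values, labelled as outside the error-controlled sequence:

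- **BioRadio respiratory measures and MBAS total:** the MMRM of SAP 15.1.3. State for each respiratory measure whether change or percent change is analysed, and check skewness for the event counts.
- **RCSS:** ANCOVA adjusted for baseline and age. This gains precision; it does not correct for dropout, and the SAP should say so.
- **CGI-C:** the age-adjusted logistic odds ratio with CI already specified for the CIC, with the missing-data rule stated so that SAP 15.2 and 15.2.2 agree.
- **SOMNOtouch measures:** leave descriptive.

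Make the change before unblinding; added later, the estimates should be labelled post hoc. The minimum alternative is to reword the objectives for these outcomes as descriptive, which removes the contradiction but gives up the estimates.

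The cost is SAP wording and more output on data already collected, with no change in sample size. Four BioRadio measures, MBAS total, RCSS and CGI-C make 7 outcomes; at two doses that is 7 × 2 = 14 intervals. They are not multiplicity-adjusted and must be presented that way.
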